Upon completion of this phase of data collection, participants will be provided with a series of validated questionnaires to complete (to be completed at every visit unless otherwise stated). These include; the International Physical Activity Questionnaire- Short Form (IPAQ-SF), Food Frequency Questionnaire (FFQ; EPIC-Norfolk; baseline and 6 months), SF-36 (36-Item Short Form Survey Instrument) and components of the Personal Diabetes Questionnaire (baseline). Participants will complete the questionnaires unassisted although members of the research team will be available to answer any questions the participant may have relating to the questionnaires. Lastly, participants will receive instructions on the use of the urine collection kit for dietary monitoring (see below) and the ActiGraph for physical activity monitoring (if randomised; see below). Participants will then be free to leave the laboratory. An additional acceptability questionnaire designed by the research team will be given to participants at the end of the 6 month visit and will include questions relating to the WARU visits, 15 minute consultation (if received), urine collection and ActiGraph use. Visits will last between approximately 120 minutes and 150 minutes depending on the time taken for participants to complete the relevant questionnaires.

Following completion of the baseline visit, participants will be randomised into either the intervention group (INT) or the control group (CON). Randomisation will be achieved using a minimisation software package (Minim) and will ensure that there will be only minor differences between groups in the variables used in the allocation process. Participants in INT will receive a focussed 15 minute one to one consultation with a practice nurse at their registered general practice. The consultation derives from the original 30 minute protocol employed during a previous study conducted by the present research team (Thatcher and Gregory, 2017) which used 104 GP-registered patients. The first half of the 30 minute consultation in that study (led by general practise) collected baseline data (height, weight, waist circumference, blood pressure)

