and the second half provided patients with lifestyle advice on preventing diabetes. The consultation to be used in the proposed study does not require general practise to collect baseline data and therefore the consultation time has been reduced from 30 minute to 15 minutes. The consultation will provide the participant with one to one information regarding the benefits of physical activity and healthy eating. Emphasis will be placed on the importance of achieving at least 150 minutes of moderate physical activity each week as well as adhering to healthy dietary habits, based on the NHS Eatwell Guide (Eatwell Guide, 2016). Furthermore, participants will have the opportunity to discuss prediabetes with a trained practice nurse and ask any questions they may have. Participants placed in CON will not receive the consultation and will only attend visits to the WARU. Due to logistical and financial implications, a subgroup of participants will also be randomised for additional physical activity monitoring. 5 participants from INT and 5 from CON will receive an Actigraph (see below for further information on the Actigraph).

Dietary Monitoring:

Metabolic fingerprinting and metabolic profiling of human urine is able to provide a comprehensive and quantitative snapshot of dietary exposure for 12 – 24 hrs prior to urine collection. While a single sample snapshot is not representative of an individuals' habitual dietary exposure, a series of snapshots over a prolonged time period can give a robust overview of an individual's nutritional health. Previous work by IBERS has demonstrated a community based urine collection protocol ($n = 16$) as a successful and non-disruptive method for monitoring habitual diet. Participants will be provided with a urine collection kit consisting of; of 14 cm non-sterile urine collection straws 4 mL additive free evacuated vacutainer tubes and a 125 mL collection container. Once urine has been collected, the sealed vacutainer tubes will be stored in an absorbent pouch within a sealed leak-proof bag and kept in the refrigerator. All urine storage equipment and instructions are fully compliant with the UN3373 standard for Category B

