Participants can choose any day within the week to begin wearing the ActiGraph but must then wear it for the following 7 days unless unfeasible to do so (e.g. swimming, bathing or showering). In this instance, participants will record at what time and the amount of time they are not wearing the ActiGraph. Should participants forget to wear the device; the same procedure will be followed. Should participants miss a whole day; they must record for an extra day directly after the 7th day. An additional sheet will be provided for participants to record any time when the device is not worn. Participants do not need to wear the ActiGraph when sleeping although they must record the time they go to sleep and at what time they wake up. Participants must fit the ActiGraph in the morning as soon as it is feasible to do so. Participants can return the ActiGraph at the end of the 7 day recording period either in person or by post.

14. Randomisation Procedure

Randomisation will be achieved using a minimisation software package (Minim) and will ensure that there will be only minor differences between groups in the variables used in the allocation process. Participant details will be recorded after the first visit and inputted into the randomisation package. Following randomisation of the first participant, remaining participants will be randomly allocated into either the intervention or control based upon age (ages 60+ in both groups / equal distribution of sex and BMI 30 kg/m² + in both groups). Randomisation will be conducted primarily by the academic supervisor. Church surgery will be informed of the patients who have been randomised to receive the intervention and referral arrangements made.

15. Baseline Data

The data to be collected at baseline and in subsequent visits are directly related to pre-diabetes or to factors which contribute to diabetes risk (e.g. dietary habits and physical activity).

- Blood test: (non-fasted) measure of glycated haemoglobin, cholesterol and metabolites indicative of dietary intake
- Anthropometry: Measures body weight and size. Being overweight is a risk factor associated with diabetes
- Blood pressure: cardiovascular health is detrimentally affected by poor lifestyle and diabetes risk
- Body composition Provides an analysis of fat mass and percentage body fat
- Urine collection: Allows for the accurate analysis of dietary behaviours
- ActiGraph: Allows for the accurate recording of physical activity

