The testing stage of this study will be defined as finished when the last participant completes the final visit (6 month testing). Additionally, the research will be stopped if there is a lack of

recruitment after 6 months or if a clinical or research incident prompts a review.

21. Statistics and Data Analysis

A computerized statistical package will be used to analyse all data associated with the primary and secondary outcomes (SPSS version 17.0, SPSS inc., Chicago, IL). Normally distributed data will be presented as mean \pm SD. Scores from the questionnaires will be calculated based upon their respective scoring protocols. A two factor mixed model ANOVA will be conducted on all physiological measures and questionnaire responses to determine any differences between groups over time. Significant differences identified by the ANOVA will be further analysed by post hoc independent or paired t-tests with Bonferroni correction. Data mining of urine samples using methods such as PCA will be employed to determine if foods can be discriminated. Statistical significance will be accepted at $P < 0.05$.

22. Sample Size Calculation

The sample size was decided based upon potential numbers of eligible patients provided to the research team by the participating general practice. Potential numbers are based upon the amount of registered patients with a $\text{BMI} > 25 \text{ kg/m}^2$ or an existing $\text{HbA1c} < 12$ months. As this is a feasibility study for a future large scale randomised control trial, no formal sample size calculation has been employed.

23. Planned Recruitment Rate

Previous work completed by the research team demonstrated an approximate 50% uptake in consultation offers in patients with pre-diabetes ($n = 420$). Our partnering surgery currently have 737 patients with a $\text{BMI} > 25 \text{ kg/m}^2$. A further 216 patients have an HbA1c (recorded within the last year) within the eligible range. Furthermore, Church surgery identifies approximately 6 new

‘at risk’ individuals each week. Therefore, we estimate it will take one month to recruit 40 patients into the study.

24. Data Management

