All electronic data will be stored on a password protected computer housed within the office of the chief researcher. Manual files will be kept locked within a filing cabinet within the office of the chief investigator. The office will remain locked when the chief investigator is not present. The chief investigator and their supervisor will be the only individuals who have direct access to the office where the data is stored. Data will be published in an anonymous form. All data handled during the study will be identified by a numeric code assigned to each participant upon entry to the study. Aberystwyth University operates its own confidentiality policy which all staff and postgraduate students are trained in. The chief investigator educational supervisor and MRes student will have access to participants’ name, contact details, and some additional personal information (e.g. age, identifying gender). The chief investigator will be responsible for communication between the participant and the research team. Participants will consent to the storage of their personal data when signing the informed consent form.

Data will be retained for 7 years following completion of the study. Anonymised data will be stored on a password protected computer accessible only to chief investigator and educational supervisor. After 7 years, the data will be deleted off of the computer hard drive. Paper based materials will be kept within locked filing cabinets within the [name] and then destroyed via confidential waste processes according to Aberystwyth University's Data Protection policy.

25. Monitoring, Audit and Inspection

The research will be monitored within the Institute of Biological, Environmental and Rural Sciences (IBERS). Regular meetings between the chief investigator ([name]), educational supervisors ([name] and [name]), MRes student ([name]) and collaborators ([name] and [name]) will ensure academic progress and rigour. Additional post-graduate monitoring is conducted regularly within Aberystwyth University by academic individuals outside of the research team. Health and Safety is overseen in IBERS by Health and Safety officers. Furthermore, regular meetings between the chief investigator, educational supervisors, MRes student and collaborators will take place every 3 months and additionally when necessary to discuss any issues that may arise and to monitor progress.

26. Ethical and Regulatory Considerations

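### The section 21 ANOVA omits the factors the arms are minimised on (age 60+, sex, BMI 30+), so its between-group tests are conservative where those factors predict outcome; the random element of the minimisation is also unstated

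*Combined protocol and SAP*

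**What the plan says.** **Allocation.** Sections 13 and 14 name a minimisation package, Minim. Section 14 reads: "Following randomisation of the first participant, remaining participants will be randomly allocated into either the intervention or control based upon age", and lists the factors in brackets as "ages 60+ in both groups / equal distribution of sex and BMI 30 kg/m² + in both groups". I read this as three binary factors: age 60 or over, sex, and BMI 30 or over. No assignment probability, tie rule or factor weights are given. On who does it: "Randomisation will be conducted primarily by the academic supervisor". Section 24 adds that "The chief investigator and their supervisor will be the only individuals who have direct access to the office where the data is stored".

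**Timing.** Section 3 (Randomisation), section 13 and section 14 all put allocation after the baseline visit. Section 12 puts consent at the start of that visit.

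**ActiGraph.** Section 13 ends the baseline visit with instructions on "the ActiGraph for physical activity monitoring (if randomised; see below", and later fixes the subgroup by arm: "5 participants from INT and 5 from CON will receive an Actigraph".

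**Analysis.** Section 21 plans a two-factor mixed ANOVA on all physiological measures and questionnaire responses "to determine any differences between groups over time", followed where significant by Bonferroni-corrected t-tests, at P < 0.05. Age, sex and BMI category do not appear in the model.

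**Size.** Section 23 refers to 40 patients. Section 22 states that there is no formal sample size calculation.

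**The concern.** Minimisation makes the arms more alike on the chosen factors than simple randomisation would. The treatment difference then varies less from trial to trial than an analysis ignorant of the factors assumes. If the factors predict the outcome, that analysis leaves their variation in the residual and reports a standard error that is too large. The intervals are too wide and power is given away, although all three factors are already recorded.

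A separate question is whether the next allocation can be foreseen. Minimisation without a random element follows from the running tallies and the next participant's profile. Someone who held both could influence booking order or the handling of borderline entrants. The plan neither excludes this setting nor describes a concealment step. Because the study exists to prepare a larger randomised trial, an unstated setting may be carried forward.

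**Working it through.** The plan gives no power or precision figure to reproduce, so the check is a calculation plus simulation.

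**Inputs from the documents:** 40 participants (section 23); 1:1 allocation (section 3 says half the cohort receives no intervention); three factors (section 14); significance level 0.05 (section 21, taken as two-sided).

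**Assumptions not in the documents:** each factor present in 50% of participants; equal weights; ties broken at random; R² of the three factors with the analysed outcome between 0 and 0.3; and, for power, a true effect of 0.9 SD, chosen to give about 80%.

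**Step 1, standard errors.** With 20 per arm and outcome SD of 1, the unadjusted SE is √(1/20 + 1/20) = 0.316. With the factors in the model it is about 0.316 × √(1 − R²). The ratio of the two is 1/√(1 − R²).

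**Step 2, actual type I error.** If the factors are almost perfectly balanced, the true SD of the unadjusted estimate is also about 0.316 × √(1 − R²). The test therefore behaves as if its critical value (t with 38 df, 2.024) were multiplied by 1/√(1 − R²).

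| R² | Adjusted SE | SE ratio | Effective critical value | Type I error, formula | Type I error, simulated |
|---|---|---|---|---|---|
| 0 | 0.316 | 1.00 | 2.024 | 0.050 | 0.051 |
| 0.1 | 0.300 | 1.05 | 2.134 | 0.039 | 0.042 |
| 0.2 | 0.283 | 1.12 | 2.263 | 0.029 | 0.030 |
| 0.3 | 0.265 | 1.20 | 2.420 | 0.020 | 0.020 |

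The simulation used deterministic minimisation and 4,000 trials per row (Monte Carlo SE √(0.05 × 0.95/4000) = 0.003). Adjusting for the factors returned the rejection rate to 0.047-0.052. With an assignment probability of 0.8 the unadjusted rates were similar: 0.041, 0.034 and 0.025 at R² of 0.1, 0.2 and 0.3.

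**Step 3, power at 0.9 SD, unadjusted then adjusted:** 0.80 and 0.79 (R² = 0); 0.81 and 0.83 (0.1); 0.82 and 0.87 (0.2); 0.82 and 0.91 (0.3).

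**Step 4, is the estimate itself noisier?** No. At R² = 0.2 its true sampling SD is 0.285 unadjusted and 0.284 adjusted. The fault lies in the reported SE.

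**Step 5, which R² applies.** For comparisons at a single visit, such as the post hoc independent t-tests, it is R² with the level of the outcome. For the group-by-time term, a factor effect that is the same at every visit cancels within person, so only R² with change over time counts. That may be smaller.

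**Step 6, predictability.** If the setting is deterministic, about 8.8 of 40 allocations are ties and stay random, so 31.2/40 = 78% are determined. Someone with the tallies and the next profile guesses (31.2 + 8.8/2)/40 = 89% correctly. Someone who knows only the arm totals guesses about 71%. With probability 0.8 there are about 6.6 ties, and the informed guess is right (33.4 × 0.8 + 6.6/2)/40 = 75% of the time. The mean difference in arm sizes rises from about 0.3 to 1.0 participants. Factor prevalences of 0.6/0.5/0.5 and 0.7/0.5/0.6 barely change the guess rates.

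**The case against.** **The analysis point is small.** The error is conservative, it depends on an R² that the documents do not supply, and at R² = 0.1 power moves only from 0.81 to 0.83. The quantified primary aims in section 4 (eligible numbers, consent and completion percentages) do not use this model. All of that stands, and it limits the importance of the point without removing it: section 21 does test between-group differences at P < 0.05, and the remedy needs no new data.

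**Stronger readings that the documents do not support.**

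- A reader might infer that allocation is random only for the first participant. Section 14 says the remaining participants are randomly allocated and never states a deterministic setting. Even in that worst case about 22% of allocations stay random through ties. What can be said is that the random element is unspecified.
- A reader might infer that allocation is predictable in practice. The 89% needs a deterministic setting, the tallies and the next profile. A supervisor may hold the last two; nothing shows that the staff who book and measure participants do. Consent and the clinic measurements come before allocation, and HbA1c is read on an automated analyser (section 19).
- A reader might infer from the ActiGraph text that the arm is known during the baseline visit. Three sections place allocation after it, the instructions come last in the visit, and the device can be worn in any week of a three-week window. This is a conflict of sequence in the wording, not evidence of early unblinding.
- A reader might want allocation held until all baseline measurement is closed. That cannot work as designed. Section 15 counts urine and ActiGraph data as baseline data, both are gathered in the three weeks after the visit, and the ActiGraph wearers are chosen by arm.

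**Conclusion.** The point holds for the analysis. The section 21 model leaves out the factors used to balance the arms, and its between-group standard errors are about 5-20% too large if those factors explain 10-30% of the variance in what is being tested. Actual type I error is then about 0.04 to 0.02 instead of 0.05. The R² range is an assumption. For the group-by-time term it must be read as R² with change over time, and at R² = 0 there is no loss. The treatment estimate is not noisier, false positives are not inflated, and the consequence is confined to secondary outcomes.

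The allocation point holds as an omission: the random element is unstated and allocation is run within the team. The 78% and 89% figures describe what would follow from a deterministic setting, not what the plan is shown to do. The ActiGraph wording needs reconciling.

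**What to change.** 1. **Section 21:** include age 60+, sex and BMI 30+ as covariates, with their time interactions, in the between-group models for the secondary outcomes, and use the same covariates in follow-up comparisons between arms. Cost: a sentence of text and a few degrees of freedom; at R² = 0 the simulated power changed only from 0.80 to 0.79.
2. **Section 14:** state the assignment probability, tie rule and factor weights, and who can see the running tallies. Set the probability below 1. A value of 0.8 is one example: informed guesses fall from about 89% to 75%, and the mean difference in arm sizes rises from about 0.3 to 1.0 participants. Cost: a software setting and wording.
3. **Sections 13 and 14:** reconcile ActiGraph instructions at the baseline visit with a subgroup defined by arm and an allocation made after the visit. One workable order is to allocate once the clinic-visit measurements and the baseline HbA1c eligibility check are recorded, then issue the ActiGraphs. Do not make allocation wait for all baseline data. Cost: wording, and a separate step for issuing the devices to ten participants.

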Participating GP surgeries will only be informed of their patient's participation in the study following receipt of informed consent. All data storage and handling will follow the principles of good clinical practice. All human tissue samples will be labelled anonymously and stored in accordance with the Human Tissue Act (2004).

4. Objectives and Outcome Measures

Primary Objectives:

The primary aim of the research is to assess the feasibility of conducting a randomised control trial to evaluate the effectiveness of a focused 15-minute one-to-one consultation in a primary care setting with a health-care professional to improve blood glucose control in pre-diabetes.

The study aims to quantify the following:

- the number of patients with an HbA1c between 42 and 47 mmolmol⁻¹ during the recruitment phase
- the percentage of patients eligible to participate who gave consent to be part of the study
- the percentage of patients who completed baseline testing; 3 month; and 6 month testing

Secondary Objectives

Secondary research questions aim to determine the impact of the consultation on the following measures at 3 and 6 months:

HbA1c

Cholesterol

BMI

Waist and hip girth

Blood pressure

Body composition

Physical activity level

Dietary habits

5. Study Design

This feasibility study will use a randomised control design to assess the effectiveness of a 15 minute one to one consultation compared to no treatment.

6. Study Setting:

All research activity included in the baseline, 3 month and 6 month visits will be completed within the [name], Aberystwyth University. The 15 minute pre-diabetes consultations will take place within Church Surgery, Aberystwyth.

7. Participant Eligibility

Participants will be eligible for participation if they are registered with Church Surgery and have an HbA1c (recorded within the last year) of between 42 and 47 mmol⁻¹.

8. Inclusion and Exclusion Criteria

Inclusion Criteria	Exclusion Criteria
Age > 18, < 80	Under judicial control
Able to provide consent	Unable to understand and follow instructions due to cognition or language problems or provide consent
Registered with a mid-Wales GP surgery	
HbA1c between 42 mmol·mol ⁻¹ and 47 mmol·mol ⁻¹	

9. Participant Identification and Recruitment

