Further information regarding the study can be sought via telephone, email or visiting the university research facility in person. Any questions the participant may have can be asked at any point prior to giving consent using any of these methods. Patients are free to withhold consent without giving reason. In accordance with the Welsh Language Act 1993, all correspondence will be translated into Welsh. For patients confirming their involvement, verbal and written informed consent will be sought in person at the start of their first visit to the Well-being Assessment Research Unit (WARU) before being inducted into the study (> 24 hours between receipt of the

study invite letter & participant information sheet and signing informed consent). Those who decline involvement will receive usual care from their GP.

13. Study Procedures

Participants will be required to visit the WARU ([name]) on 3 separate occasions, for baseline, 3 month and 6 month testing. During the baseline visit, the procedures and protocol of the study will be explained and informed consent will be received. Participant's height (Holtain Ltd, Crymych, UK) and body mass (wearing loose fitting clothing; Seca 899, Hamburg, Germany) will be collected to calculate body mass index (BMI) and waist and hip girth recorded (Seca 201, Seca GmbH & Co, Hamburg, Germany). Next, participants will be asked to sit quietly for 10 minutes in the laboratory before blood pressure is recorded from the upper non-dominant arm (Omron M3, Omron Healthcare Ltd, Milton Keynes, UK). Participants will remain seated prior to a 6 mL blood sample being obtained from the antecubital vein and collected into a heparinised vacutainer (BD Vacutainer Systems, Plymouth, UK), with minimal stasis, using standard venepuncture methods performed by a trained member of the research team. Should patients HbA1c be outside the required values during the baseline visit, they will be informed and will take no further part in the research. WARU will inform the participant's GP if their HbA1c is indicative of diabetes. Body composition will be analysed using bioelectrical impedance (Bodystat 1500, Bodystat Ltd, Douglas, British Isles).

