Administration of the International Physical Activity Questionnaire Short Form	3	10 minutes	[name] or other member of the research team. This will take place in the [name] at Aberystwyth University
Administration of the Food Frequency Questionnaire	2	15 minutes	[name] or other member of the research team. This will take place in the [name] at Aberystwyth University
36-Item Short Form Health Survey Instrument	3	10 minutes	[name] or other member of the research team. This will take place in the [name] at Aberystwyth University
Components of the Personal Diabetes Questionnaire	1	10 minutes	[name] or other member of the research team. This will take place in the [name] at Aberystwyth University
15 minutes pre-diabetes consultation (if randomised to receive)	1	15 minutes	Performed by a practice nurse at a mid-Wales General Practise
End of Study Feedback questionnaire	1	10 minutes	[name] or other member of the research team. This will take place in the [name] at Aberystwyth University

18. Withdrawal Criteria

Participants are free to withdraw from the study at any time without giving prior warning or reason for withdrawal. Participants will not be replaced if withdrawn. Recruitment will continue for the first 6 months of the study. New participants will receive unique individual participant numbers.

19. Storage and Analysis of Clinical Samples

Blood Treatment:

A 1 mL aliquot of whole blood will be transferred from the heparinised vacutainer into a 1.5 mL Eppendorf. The remaining whole blood will be centrifuged at 1500 g for 10 minutes at 4°C. The separated plasma will be pipetted evenly into two separate eppendorfs and frozen at -80°C for subsequent analysis of metabolic content using FIE-MS and GC-MS. Two 1.5 µL aliquots of whole blood will be transferred from the 1.mL aliquot into separate test cartridges and will be analysed for HbA1c and lipid profile by an automated point of care blood analyser (Afinion 2, Abbot, Cheshire, UK).

Urine Treatment:

Urine samples will be centrifuged at 1500 g for 10 minutes at 4°C. 1ml of supernatant will be pipetted evenly into two separate eppendorfs and frozen at -80°C prior to analysis of metabolic content using FIE-MS and GC-MS.

20. End of Trial

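### Baseline HbA1c is known before allocation but is neither a minimisation factor nor an analysis covariate, which costs precision in the secondary HbA1c comparison

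*Combined protocol and SAP*

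**What the plan says.** Section 14 allocates by minimisation with the Minim package. After the first, participants "will be randomly allocated into either the intervention or control based upon age (ages 60+ in both groups / equal distribution of sex", with BMI of 30 or more as the third factor. Sections 13 and 14 both state what this buys: it "will ensure that there will be only minor differences between groups in the variables used in the allocation process". HbA1c is not one of those variables.

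The value is available in time. Section 19 says whole blood from each visit "will be analysed for HbA1c and lipid profile by an automated point of care blood analyser". Section 13 uses the result as a gate: "Should patients HbA1c be outside the required values during the baseline visit, they will be informed and will take no further part". Allocation comes later: "Following completion of the baseline visit, participants will be randomised into either the intervention group (INT) or the control group (CON".

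Section 4 makes feasibility the primary aim and lists HbA1c first among the secondary measures. The trial being prepared concerns blood glucose control. Section 21 plans a two-factor mixed ANOVA (group by time) on all physiological measures. Significant findings are followed by independent or paired t-tests with Bonferroni correction. No baseline covariate is named.

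**The concern.** Baseline HbA1c is likely to be among the strongest predictors of HbA1c at 3 and 6 months. Age, sex and BMI are balanced, while the baseline value of the outcome the future trial is about is left to chance in a study of about 40. The analysis does not remove the resulting gap. A comparison of arms at follow-up carries part of it in one direction, and a comparison of change carries the rest in the other. The two can therefore disagree because of the draw alone. At stake is the precision of the HbA1c estimate handed to the future trial, and how that estimate reads in the one allocation that is realised. Allocation cannot be repaired afterwards, though the analysis can.

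**Working it through.** The plan gives no power, effect size or SD, so there is no figure to reproduce.

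**Inputs from the document**
- 40 participants (Section 23, a recruitment estimate). Half do not receive the intervention (Section 3), so n = 20 per arm.
- HbA1c entry range 42 to 47 mmol/mol (Sections 4, 8 and 13).

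**Assumptions (not in the document)**
- SD of baseline HbA1c. Integer values uniform on 42 to 47 give √((6² − 1)/12) = 1.71; a distribution skewed towards 42 gives about 1.60. Wider range shown: 1.0 to 2.5.
- Baseline-to-follow-up correlation ρ of 0.3 to 0.7, equal SDs at both times (so slope = ρ).
- In simulation: three two-level factors independent of HbA1c; deterministic allocation or a 0.8 biased coin.

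**Step 1: size of the chance gap.** SE of the difference in baseline means = SD × √(2/20).

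| SD | SE of gap | 95% range |
|---|---|---|
| 1.0 | 0.32 | ±0.62 |
| 1.44 | 0.46 | ±0.89 |
| 1.71 | 0.54 | ±1.06 |
| 2.5 (extreme for this range) | 0.79 | ±1.55 |

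At SD 1.71 the median absolute gap is 0.674 × 0.54 = 0.36. Simulated 40-patient trials with SD 1.6 to 1.7 agree:

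| Minimisation factors | SD of gap | 95% of trials within | Gap of 1.0 or more |
|---|---|---|---|
| Age, sex, BMI | 0.51-0.55 | 1.0-1.1 | about 6-8% |
| Plus HbA1c 42-44 v 45-47 | 0.28-0.35 | 0.55-0.70 | 0.5% or fewer |

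**Step 2: how a gap D carries over.**
- Follow-up comparison: ρ × D.
- Change from baseline: ρ × D − D = −(1 − ρ) × D.
- Baseline-adjusted comparison: 0.

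For D = 1.0 and ρ from 0.3 to 0.7, the follow-up comparison shifts by +0.3 to +0.7 and the change comparison by −0.7 to −0.3. For the median gap at ρ = 0.6, the shifts are 0.6 × 0.36 = +0.22 and −0.4 × 0.36 = −0.14.

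**Step 3: precision.** Simulated SE of the arm comparison in mmol/mol (SD 1.71, deterministic minimisation):

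| ρ | Follow-up, now → with HbA1c factor | Change, now → with HbA1c factor | Adjusted, now → with HbA1c factor |
|---|---|---|---|
| 0.3 | 0.55 → 0.52 | 0.64 → 0.55 | 0.53 → 0.52 |
| 0.5 | 0.55 → 0.49 | 0.53 → 0.49 | 0.47 → 0.47 |
| 0.7 | 0.54 → 0.43 | 0.42 → 0.40 | 0.39 → 0.39 |

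Adjustment alone is about as good as, or better than, the extra factor alone. With adjustment in place, the extra factor adds almost nothing.

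**Step 4: balancing without adjusting.** With HbA1c in the minimisation and slope 0.6, the true SE of the follow-up comparison falls from about 0.55 to 0.47-0.48. The ordinary t-test still reports about 0.54, because its SE ignores the balancing. Its type I error drops to about 2.4-3.0% against a nominal 5%, so the gain in precision is not credited.

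**The case against.** The strongest defence is that this is a permissible choice. The plan promises balance only on the variables used and contradicts nothing by omitting HbA1c. The narrow entry range itself limits the gap. Section 22 states that no formal sample size calculation was made, HbA1c is one of eight secondary measures, and the main analysis is the mixed ANOVA, with t-tests only as a conditional step. All of that stands, and it limits the weight of the point.

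Four stronger readings are tempting, and the documents do not support them.
- **That the HbA1c result is biased.** The imbalance arises by chance. It does not bias the estimate across randomisations or inflate the unconditional type I error, and the SE of the unadjusted comparison already reflects it.
- **That the whole gap passes into the arm comparison.** Only the fraction ρ does so at follow-up, and the change contrast moves the other way. A gap of 1.0 is a tail case.
- **That balancing by design adds useful precision even under baseline adjustment.** The adjusted SE is essentially the same with and without the extra factor.
- **That the feasibility results are compromised.** The counts in range and the consent and completion percentages in Section 4 do not depend on the minimisation factors.

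What the defence does not answer is that neither the allocation nor the planned analysis uses a baseline value already in hand.

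**Conclusion.** The point holds as a low-cost improvement in precision, not as a validity failure. Baseline HbA1c is known before allocation and used in neither Section 14 nor Section 21. The chance gap has an SD of about 0.5 mmol/mol, typically about 0.36. At ρ = 0.5, using baseline HbA1c would cut the SE of the HbA1c comparison from about 0.53-0.55 to 0.47. The size rests on 20 per arm, an assumed SD of 1.6 to 1.7 and the assumed correlation. At SD 1.0 the 95% range of the gap shrinks to ±0.62. That the omission exists, and the direction of its effect, do not depend on those assumptions.

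**What to change.** Make two changes together.

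1. **Section 14:** add baseline HbA1c (42-44 v 45-47 mmol/mol, from the reading taken at the baseline research-unit visit) as a fourth Minim factor, entered with the other details after that visit.
2. **Section 21:** compare the arms on 3- and 6-month HbA1c, adjusting for baseline HbA1c and the minimisation factors.

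If only one is made, it should be the second: it delivers most of the gain. The first should not be made without it, for the reason in step 4 of the working.

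**Cost:** one more field in software already in use, no new data, and a few degrees of freedom in the model. Balance on the other factors loosens slightly. In simulation the mean worst imbalance across age, sex and BMI rose from 5.1 to 5.8 percentage points with deterministic allocation, and from 8.4-8.5 to 9.5-9.6 with a biased coin.
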